7.6 Subgroup Analysis

Summary tables will be produced for the predefined subgroups, and the interactions between treatment and these subgroups will be analyzed using a Cox proportional hazards model. Individual models will be utilized for each interaction to assess the statistical significance. The results will also be depicted graphically in a forest plot. The modification of treatment effects on the primary outcome will be investigated within the following subgroups:

- ✓ Age, <65 years old vs. \geq 65 years old;
- ✓ Sex, men vs. Women;

- ✓ Hypertension, yes vs. no;
- ✓ Diabetes, yes vs. no;
- ✓ Current smoking, yes vs. no;
- ✓ Body mass index (BMI), $<25 \text{ Kg/m}^2$ vs. $\geq 25 \text{ Kg/m}^2$;
- ✓ Latest qualifying event, ischemic stroke vs. TIA;
- ✓ Time from latest ischemic event to enrollment, ≤ 2 weeks vs. >2 weeks, ≤ 6 weeks vs. >6 weeks;
- ✓ Occurrence of the qualifying event, first-onset vs. recurrent;
- ✓ Symptomatic qualifying artery, anterior circulation vs. posterior circulation;
- ✓ ASPECTS or pc-ASPECTS, 10 vs. 6-9.

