3.2.1 Inclusion criteria

Patient eligibility for study enrollment is determined based on the following inclusion criteria:

- (1) Age ranging between 18 and 80 years.
- (2) sNA-IAO defined as:
 - ① Time from latest ischemic event (ischemic stroke or TIA) in territory of the qualifying artery to enrollment is beyond 24 hours and within 90 days.
 - ② Occlusion of intracranial ICA, M1 segment of MCA, intracranial VA (with contralateral VA hypoplasia or occlusion) or BA confirmed by computed tomographic angiography (CTA) or digital subtraction angiography (DSA).
- (3) Computed tomographic (CT) or magnetic resonance imaging (MRI) demonstrating Alberta Stroke Program Early CT Score (ASPECTS) ≥ 6 (for anterior circulation) or Posterior Circulation Alberta Stroke Program Early CT Score (pc-ASPECTS) ≥ 6 and pons-midbrain index (PMI) < 3 (for posterior circulation).
- (4) Modified Rankin Scale (mRS) score 0-2 at the time of enrollment.
- (5) Technical feasibility of endovascular recanalization for the qualifying artery evaluated by two experienced interventional neuroradiologists.
- (6) More than one risk factor for atherosclerosis.

(7) Signed informed consent form.

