3.16.5 Statistical Significance and Software

All statistical tests are performed by 2-sided tests. A 2-sided P value less than 0.05 is considered to demonstrate a statistically significant difference. All analyses will be performed with SAS software version 9.4 (SAS Institute).

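### Effect modification by time from event, age and BMI is tested only on binary cuts, and time on two overlapping cuts with no lead test; a continuous interaction would usually use the data better

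*SAP*

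**What the plan says.** SAP 7.6 lists the subgroups for the primary outcome, and Protocol 3.16.3 gives the same list. Age enters as a split at 65 ("Age, <65 years old vs" 65 or over), BMI as a split at 25 kg/m², and the two imaging scores as "ASPECTS or pc-ASPECTS, 10 vs. 6-9". Time is listed as "Time from latest ischemic event to enrollment, ≤ 2 weeks vs. >2 weeks, ≤ 6 weeks vs. >6 weeks", which is two binary splits of one variable.

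The test is a treatment-by-subgroup term in a Cox model: "Individual models will be utilized for each interaction to assess the statistical significance". SAP 7.1 likewise describes the assessment as comparing the treatment effect across subgroup levels, and it plans no multiplicity adjustment. Protocol 3.16.5 sets the threshold: "A 2-sided P value less than 0.05 is considered to demonstrate a statistically significant difference".

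The underlying variables have a range. Protocol 3.2.1 admits patients whose interval from the event "is beyond 24 hours and within 90 days", and sets "Age ranging between 18 and 80 years". Neither document plans a continuous, trend or spline interaction, gives a reason for any cut point, or says which of the two time splits answers the question.

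**The concern.** How the effect of recanalisation varies over an entry window of about 1 to 90 days is a natural question for this cohort. The plan addresses it with two tests that share patients. Everyone beyond 6 weeks is also beyond 2 weeks, and everyone within 2 weeks is also within 6 weeks. The 2-6 week patients are pooled with the late group in one model and with the early group in the other. If one P value falls below 0.05 and the other does not, the plan does not say what is concluded.

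The second issue is efficiency. Replacing a continuous modifier by a yes/no indicator discards the variation within each half. If the effect changes gradually, the split test is weaker than a test on the measured value, and a real gradient is more easily missed.

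**Working it through.** **Inputs from the documents:** two-sided alpha 0.05; time from just over 1 day to 90 days, cut at 14 and at 42 days; age 18-80, cut at 65; BMI cut at 25. The documents state no power, event count, interaction size or distribution, so there is no planned figure to reproduce. Everything below rests on stated assumptions.

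**1. Information kept by a cut.** If the log hazard ratio changes linearly with the modifier, the share of information kept is the squared correlation r² between the modifier and its binary version. For a uniform modifier with a proportion p below the cut, r² = 3p(1 − p).

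- 2 weeks: p = (14 − 1)/(90 − 1) = 13/89 = 0.146; r² = 3 × 0.146 × 0.854 = 0.374. Kept 37%, lost 63%.
- 6 weeks: p = (42 − 1)/89 = 41/89 = 0.461; r² = 3 × 0.461 × 0.539 = 0.745. Kept 75%, lost 25%.

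For equal power the cut tests therefore need 1/0.374 = 2.7 and 1/0.745 = 1.3 times as many events.

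**2. Other assumptions for time.** With right-skewed time (exponential with 30-day parameter, truncated to 1-90 days) and a linear gradient, the cuts keep 48% (2 weeks) and 69% (6 weeks). If the gradient is linear in log time, they keep 65% and 58% under uniform time, and 69% and 39% under the skewed one. Over a wider set of skewed distributions with a linear gradient, the loss ran from 36% to 71% at 2 weeks and from 27% to 72% at 6 weeks.

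**3. Age and BMI.** For a normal modifier cut at standardised distance z from the mean, r² = φ(z)²/[Φ(z)(1 − Φ(z))].

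- Age, assumed mean 60 and SD 10: z = 0.5; r² = 0.3521²/(0.6915 × 0.3085) = 0.58, so 42% lost. Truncating at 18-80 gives about 44%. With mean 65 the loss is about 35-36%. With mean 50 it is 66-84%, so the result depends on the cohort.
- BMI, assumed mean 25.5 and SD 3.3: z = −0.15; r² = 0.63, so 37% lost. With SD 3.2 and means from 23 to 27, the loss is 36-45%.

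**4. From information to power.** If the continuous test has noncentrality δ, the cut test has δ√r², and its power is Φ(δ√r² − 1.96) + Φ(−δ√r² − 1.96).

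| Power of continuous test | δ | Power at 6-week cut (r² 0.745) | Power at 2-week cut (r² 0.374) | Points lost |
|---|---|---|---|---|
| 80% | 2.80 | 67.7% | 40.3% | 12.3 and 39.7 |
| 50% | 1.96 | 39.4% | 22.4% | 10.6 and 27.6 |
| 30% | 1.43 | 23.6% | 14.2% | 6.4 and 15.8 |
| 20% | 1.11 | 16.1% | 10.5% | 3.9 and 9.5 |

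**5. Which row is realistic?** As an illustration, assume 1:1 groups, a 50/50 split and an interaction variance of 16/events. With 60 events and a ratio of hazard ratios of 2.0, the cut test has 27% power, against 34% for a continuous test if 25.5% of the information is lost (7 points) or 39% if 36.3% is lost (12 points). With 40 events it has 20%, against 25% or 28% (5 to 8 points).

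**6. If the truth is a step.** A cut placed exactly at the step loses nothing. A log-time term would then keep 65% (step at 2 weeks) or 58% (step at 6 weeks) under uniform time, and 69% or 39% under the skewed distribution. The plan's other cut also suffers: for a step at 2 weeks under uniform time, the 6-week cut keeps p₁(1 − p₂)/[p₂(1 − p₁)] = (0.146 × 0.539)/(0.461 × 0.854) = 20%.

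**The case against.** The strongest reply is that the better test depends on a shape nobody knows. If the effect changes abruptly at a threshold, the cut is the right model and a log-time term can lose more than half the information. This stands, and it is why the cuts should stay in the report and the continuous test needs a shape check. It does not rescue the plan for time, because naming two thresholds commits to neither, and a cut away from the step can perform very badly.

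The subgroups are also prespecified, identical in both documents and tested by formal interaction rather than by comparing within-group P values. That is good practice, and it stands. SAP 7.1 names one primary variable and one treatment comparison, so nothing here touches the main result.

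A reader might infer that every one of these interaction tests loses at least 10 points of power. The documents do not support that. They give no interaction power, and for the 6-week cut under uniform time the loss reaches 10 points only if the continuous test has about 47-90% power. A study with few events would probably sit below that range.

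A reader might also extend the percentages to "ASPECTS or pc-ASPECTS, 10 vs. 6-9". That is not supported either. The two scores are different scales for different circulations and their distributions are not given, so no loss is claimed for them here.

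**Conclusion.** The point holds as a conditional one. What needs no assumption is that time, age and BMI are tested only on binary cuts, that time has two overlapping cuts with no lead, and that the 2-6 week patients are never separated. The size of the loss is assumption-based. With roughly linear modification it is about 25-65% of the information (uniform time: 25% at 6 weeks and 63% at 2 weeks; age and BMI about 35-45% under central assumptions), and some plausible distributions fall outside that range. This means about 12-40 power points if the continuous test had 80% power and about 4-10 if it had 20%. It means no loss if the truth is a step at the cut tested.

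It would go too far to call the cuts the weakest possible analysis, or to predict that the report will claim consistency across subgroups: the first depends on the unknown shape, and neither document contains such a conclusion. The analyses are exploratory and the primary result is unaffected. This is a cheap improvement.

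**What to change.** In SAP 7.6 and Protocol 3.16.3:

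- For time from event, age and BMI, make treatment × the continuous variable the lead interaction test, one per variable. Use log time, with a spline or the three-group version as a check on shape.
- Keep the existing cuts in the forest plot as descriptive results, and show time as three non-overlapping groups: up to 2 weeks, over 2 to 6 weeks, and over 6 weeks.
- For ASPECTS and pc-ASPECTS, optionally report a trend interaction separately within each circulation, since the scales should not share one term.

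The cost is SAP wording and a few model statements. No new data are needed, because the underlying values are required to form the cuts. The downside is an assumed shape, which can miss a step or a U-shaped pattern; the spline or three-group check guards against this for time. If outcomes have already been analysed, add the continuous tests and label them supplementary.

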7.7 Secondary Outcomes

Time-to-event secondary outcomes will be evaluated using Kaplan-Meier survival analysis and Cox regression model. HR between the two groups and its 95% CI will be calculated using a Cox proportional hazards regression model. Non-time-endpoints of the secondary outcomes will be evaluated using logistic regression model. The 1-year mRS score will be analyzed using ordinal logistic regression to estimate the common odds ratio (OR). The 1-year EQ-5D scores will be compared between groups using general linear regression analysis.

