Secondary Endpoints	
Secondary outcomes as follows:
 
 • Mortality within 1 year; • Ischemic stroke outside the territory of the qualifying artery within 1 year; • Disabling stroke within 1 year; • TIA in the territory of the qualifying artery within 1 year; • Unplanned revascularization (EC-IC bypass surgery or ER) of the qualifying artery within 1 year; • Myocardial infarction within 1 year; • Composite vascular events within 1 year, including any stroke, myocardial infarction, and unplanned revascularization; • Quality of life assessment (EuroQol-5-Dimensions scale questionnaire) at 1 year; • mRS score at 1 year; • Periprocedural outcomes; • Restenosis or reocclusion (symptomatic or asymptomatic).
Statistical Methods	
 • Categorical variables will be compared between treatment groups using χ^2 or Fisher's exact test. Continuous variables or ordinal variables will be compared between treatment groups using t-test or Wilcoxon-Mann-Whitney test. • The primary and time-to-event secondary outcomes will be compared between the groups using log-rank test. • Kaplan-Meier curves will be used to show the incidence of outcomes over time. • The hazard ratio (HR) and adjusted hazard ratio (aHR) between groups, along with their 95% CIs, will be determined using univariate and multivariate Cox proportional hazards regression models. • Propensity score matching (PSM) will be performed to reduce the possible influence of selection bias and confounders on the outcomes. • A 2-sided P value less than 0.05 is considered to demonstrate a statistically significant difference. • All analyses will be performed with using SAS Version 9.4.

Schedule of assessments

Table 1: Summary of Study Treatment and Study Assessments

Study Requirements	Screening and Baseline	Endovascular recanalisation			Discharge	Follow-up Visits		
		Pre-procedure	Intra-procedure	Post-procedure		30-Day (±7 days)	90-Day (±7 days)	1-Year (±30 days)
Inclusion/Exclusion	X	X						
Informed Consent	X							
Clinical Assessment, Vital Signs, and Physical Exam	X	X			X	X	X	X
Laboratory tests	X					X	X	X
NIHSS (blinded to treatment)	X				X	X		
mRS (blinded to treatment)	X				X	X	X	X
EQ-5D (blinded to treatment)						X	X	X
mTICI assessment		X	X	X				
CT/MRI	X			X			X	X
CTP/PWI	X						X	X
CTA/DSA	X						X	X
Protocol Deviations		X	X	X	X	X	X	X
Medication review and patient compliance survey	X	X	X	X	X	X	X	X

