3.6 Treatments and Study Groups

The technical feasibility of endovascular recanalization for all sNA-IAO patients in this study will be collaboratively evaluated by two experienced interventional neuroradiologists. The decision to select either medical treatment alone or additional ER is made by the patients themselves or their legal representatives. Patients are subsequently divided into two groups according to the treatment they received: the medical group and the endovascular recanalization (ER) group. Patients in ER group will receive endovascular recanalisation procedure (details in procedure part below) plus medical treatment (same as the control group).

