To investigate whether endovascular recanalisation plus medical treatment is superior to medical treatment alone for symptomatic non-acute intracranial artery occlusion (sNA-IAO) in the primary outcome (any stroke or death within 30 days after enrollment or ischemic stroke in the territory of the qualifying artery from 30 days to 1 year after enrollment).

3. Statistical Hypotheses

The primary hypothesis is:

Patients in the endovascular recanalisation group are expected to demonstrate a lower incidence of primary outcome (any stroke or death within 30 days after enrollment or ischemic stroke in the territory of the qualifying artery from 30 days to 1 year after enrollment).

4. Study Design

The Endovascular Recanalization for Non-Acute Intracranial Artery Occlusion (ERNA-IAO) study is a multicenter, prospective, cohort study, this cohort prospectively enrolls consecutive patients with radiologically confirmed sNA-IAO at 6 comprehensive stroke centers in China from January 1, 2020 to October 31, 2023. All study centers were required to have performed at least 120 endovascular procedures annually, including at least 40 cases of endovascular interventions involving intracranial arteries. The interventional neuroradiologists at these centers had each performed over 100 endovascular procedures. All participants or their legal representatives provide written informed consent prior to enrollment. The technical feasibility of endovascular recanalization for all sNA-IAO patients in this study will be collaboratively evaluated by two experienced interventional neuroradiologists. The decision to select either medical treatment alone or additional endovascular recanalization is made by the patients themselves or their legal representatives. Patients are subsequently divided into two groups according to the treatment they received: the medical group and the endovascular recanalization group. The study protocol was approved by the Institutional Ethics Committee of Beijing Tiantan Hospital, (approval number: KY2020-114-02), and each subcenter, and will follow the STROBE (Strengthening the Reporting of Observational Studies in Epidemiology) guideline.

Endovascular recanalization (ER):

Patients will receive ER (details in procedure part in Supplement 1) plus medical treatment (same as the control group). All procedures are performed under general anesthesia by an experienced interventional neuroradiologist.

Medical treatment:

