7.5 Primary Efficacy Outcome

The difference in primary outcome between groups was assessed using Kaplan-Meier analysis and compared via log-rank test. Hazard ratio (HR) between the two groups and its 95% CI will be calculated using a Cox proportional hazards regression model. Furthermore, a multivariate Cox proportional hazards model will be used to perform multivariable adjustment for the primary outcome, yielding the adjusted hazard ratio (aHR) and its 95% CI.

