7.5 Safety Analyses

Summary tables and data displays will be provided for adverse events as well as serious adverse events (as detailed in the study protocol). Procedure-related complications in the endovascular recanalization group will be analyzed. The Chi-square test or Fisher's exact test will be used to compare the incidence of adverse events and serious adverse events between the treatment groups.

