7.6 Propensity Score Matching Analysis

Propensity score matching (PSM)² will be performed to reduce the possible influence of selection bias and confounders on the outcomes. A PSM cohort will be established in a 1:1 ratio based on the nearest-neighbor matching algorithm with a caliper width of 0.2 of the propensity score with main variables associated with the primary outcome as covariates. Statistical analysis methods for baseline characteristics and outcome will remain consistent before and after PSM.

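### In the full cohort the SAP plans no covariate-adjusted estimate for secondary or safety outcomes, although patients choose their treatment and the primary outcome is adjusted

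*SAP*

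**What the plan says.** Allocation is not randomised. Protocol 3.6 states: "The decision to select either medical treatment alone or additional ER is made by the patients themselves or their legal representatives". SAP section 4 says the same.

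For the primary outcome, SAP 7.5 (Primary Efficacy Outcome) plans a Kaplan-Meier analysis, a log-rank test and a Cox hazard ratio. It then adds a second step: "a multivariate Cox proportional hazards model will be used to perform multivariable adjustment for the primary outcome", which gives an adjusted hazard ratio (aHR).

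For the secondary outcomes, SAP 7.7 (Secondary Outcomes) states: "Time-to-event secondary outcomes will be evaluated using Kaplan-Meier survival analysis and Cox regression model". The effect measure is then given as "HR between the two groups and its 95% CI will be calculated using a Cox proportional hazards regression model". No aHR and no covariates are named. The ordinal model for 1-year mRS, the linear model for EQ-5D and the logistic models for the remaining endpoints also carry no covariates.

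For safety, SAP 7.5 (Safety Analyses) says that a chi-square or Fisher's exact test "will be used to compare the incidence of adverse events and serious adverse events between the treatment groups".

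SAP 7.6 (Propensity Score Matching Analysis) plans a 1:1 matched cohort that "will be performed to reduce the possible influence of selection bias and confounders on the outcomes". The same outcome methods are to be applied before and after matching. The matching covariates are described only as the main variables related to the primary outcome.

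**The concern.** The SAP accepts that patient choice can confound the comparison, and it acts on this for the primary outcome in the full cohort. It does not do so for the outcomes a reader will weigh against any benefit. This matters here because of how the primary outcome is built: after day 30 it counts only ischemic stroke in the territory of the qualifying artery. Later deaths, hemorrhagic strokes and strokes in other territories enter only through the secondary and safety outcomes. The Protocol's Background itself raises safety concerns about recanalization in non-acute occlusion.

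If the plan is followed as written, a healthier or sicker recanalization group could look safer or more dangerous in the full cohort for that reason alone, while the primary hazard ratio beside it has been adjusted.

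**Working it through.** The documents state no figure on this point, so there is none to reproduce. The check is mainly a comparison of text.

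**1. SAP 7.5 against SAP 7.7.** The two sections give nearly the same sentence for the Cox hazard ratio and its 95% CI. Section 7.5 continues with a multivariable model and an aHR; section 7.7 does not. Side by side, the natural reading is that the secondary Cox models contain treatment group only.

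**2. Safety.** Chi-square and Fisher's exact tests on a two-group table cannot take covariates.

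**3. What matching adds.** SAP 7.6 (Propensity Score Matching Analysis) refers to outcomes in the plural and keeps the methods unchanged after matching. The secondary hazard ratios are therefore repeated in the matched cohort, and safety outcomes, which are section 5.3 within SAP section 5 (Outcomes), are most naturally included. Three limits remain:
- The covariates are unlisted and chosen by their relation to the primary outcome. A factor that predicts 1-year death or myocardial infarction but not the primary composite can be left out.
- 1:1 caliper matching can discard patients, which costs most for rare outcomes.
- The SAP does not say whether the full-cohort or the matched estimate is to be read as the confounding-controlled one.

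**4. Protocol against SAP.** Protocol 3.16.2, whose heading covers primary and secondary outcomes, plans HR and aHR from univariate and multivariate Cox models without naming an outcome. A separate sentence then gives the time-to-event secondary outcomes Kaplan-Meier and a Cox model, with no aHR. In the synopsis, an unrestricted HR/aHR bullet comes shortly after "The primary and time-to-event secondary outcomes will be compared between the groups using log-rank test". The Protocol can be read either way.

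**5. Possible size.** All inputs below are assumptions. Take one binary prognostic factor with hazard ratio H, present in proportion p1 of one group and p0 of the other, and no true treatment effect. The approximate distortion of the crude hazard ratio, when events are uncommon, is

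B = [1 + p1(H − 1)] / [1 + p0(H − 1)]

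| H | p1 | p0 | B | Groups reversed (1/B) |
|---|---|---|---|---|
| 1.5 | 0.40 | 0.30 | 1.20/1.15 = 1.04 | 0.96 |
| 2 | 0.50 | 0.30 | 1.50/1.30 = 1.15 | 0.87 |
| 3 | 0.60 | 0.30 | 2.20/1.60 = 1.38 | 0.73 |

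The first row is negligible and the last is material. The documents do not show which is closer to this cohort.

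**The case against.** A reader might infer that the secondary outcomes receive nothing but crude hazard ratios. The documents do not support that: the matched analysis is aimed at outcomes in general and repeats the same methods, so matched hazard ratios for death, disabling stroke and the rest are planned. A reader might also infer that the SAP contradicts a broader Protocol. That is too strong as well. SAP 7.7 repeats the Protocol 3.16.2 sentence on time-to-event secondary outcomes, and the scope of the Protocol's aHR is ambiguous rather than plainly wider.

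Other fair points:
- SAP 7.7 never says univariate, so the absence of covariates is inferred from silence. The contrast with 7.5 makes the inference reasonable, but it remains one.
- The safety point partly repeats the mortality and disabling-stroke point, because the SAP says serious adverse events here are chiefly disabling strokes, symptomatic intracranial hemorrhages and deaths. Symptomatic intracranial hemorrhage is the main addition.
- The bias figures rest on assumed inputs and would apply to any unadjusted observational hazard ratio. They describe the full-cohort estimate, not the matched one.
- Extending the 7.5 model to other outcomes would settle little by itself, since 7.5 names no covariates.

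These points narrow the concern to the full cohort and shape the fix. They do not remove it: matching is the only confounding control the SAP specifies for these outcomes, and it is built around a different outcome.

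**Conclusion.** The point holds for the full cohort. As written, the SAP specifies no covariate-adjusted estimate there for any secondary outcome and compares serious adverse events by unadjusted tests, while the primary outcome is adjusted. Control of confounding for these outcomes rests on the matched cohort alone, whose covariates may not suit them. Whether the Protocol intends an aHR for secondary outcomes is unclear.

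The conclusion rests on reading SAP 7.7 by contrast with SAP 7.5, and on treatment being chosen rather than assigned. The size is unknown; the illustrative range of 1.04 to 1.38 (reciprocals 0.96 to 0.73) depends wholly on assumed inputs. This should be corrected because these outcomes carry much of the benefit-harm judgement and the change is small. It does not undermine the primary analysis.

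**What to change.** In SAP 7.7:
- Report an adjusted estimate beside the crude one for each between-group secondary outcome: an aHR for time-to-event outcomes, an adjusted common odds ratio for mRS, an adjusted difference for EQ-5D, and an adjusted odds ratio where logistic regression is used. In the safety section, do the same for any serious adverse event.
- Prespecify the covariates from baseline data already collected, for example age, sex, hypertension, diabetes, smoking, type of qualifying event, time from event to enrollment, anterior or posterior circulation, ASPECTS or pc-ASPECTS, and baseline mRS and NIHSS.
- Where events are few, adjust for a propensity score built from that same set, entered as a single covariate. The score as now described, tied to the primary outcome, should not be reused for this.
- Label crude full-cohort estimates as descriptive.

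In SAP 7.6 (Propensity Score Matching Analysis), state that the matched analysis covers all secondary and safety outcomes. In Protocol 3.16.2 and the synopsis, state which outcomes receive an aHR.

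The cost is revised wording and additional model runs, with no new data collection. The drawback is somewhat wider or less stable intervals for rare outcomes such as death, myocardial infarction or unplanned revascularization. With no event counts in the documents, that loss cannot be quantified.

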7.2 Data Handling Conventions

Premature withdrawal and missing data

If any subject withdraws prematurely from the study (prior to the final visit), they are required to complete the withdrawal visit in the case report form (CRF). The reasons for withdrawal will be presented in a summary table. For the purposes of summaries and analysis of clinic visit data, this visit will be assigned to the next scheduled clinic visit for that subject, regardless of whether the date falls within the next visit window.

Efforts will be undertaken at study sites to reduce the amount of missing data. For the primary efficacy outcome, multiple imputations in a model including strong prognostic variables will be used. Also, sensitivity analyses will be undertaken to explore the effect of missing data on the endpoint and test the robustness of the estimate. Ultimately, only patients who entirely completed the 1-year follow-up are included in the final analysis.

Event rates

The number of people and person-time of events should be recorded in detail and showing the event rate of each treatment group in summary statement.

The event rate for each treatment group will be calculated as: the sum of number of event for all the patients/the sum of number of treatment periods for all the patients.

Time to event analysis

Differences between treatments in the risk of any stroke (ischemic or haemorrhagic) event or composite vascular events during follow-up will be assessed using standard Kaplan-Meier time-to-event approaches. The time to the first event will be used in the model when there are multiple events of the same type. Patients will be considered censored at the time of study termination or death if there are no events occurred during the study.

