7.4 Demographic and Baseline Characteristics

The following demographic information baseline characteristics, such as age, sex, medical history, smoking history, alcohol history, treatment history, qualifying ischemic event characteristics, Alberta Stroke Program Early CT Score (ASPECTS) for anterior circulation stroke as well as posterior circulation ASPECTS (pc-ASPECTS), baseline mRS score and NIHSS score, will be listed and summarized for subjects in each treatment group.

The continuous data followed normal distribution will be presented as mean and standard deviation, and the continuous data followed skewness distribution will be presented as median and interquartile range; categorical data will be presented as n (%). T-test or Wilcoxon-Mann-Whitney test will be used for comparison between two continuous data, and Chi-squared tests, Fisher exact test will be used for comparison between two categorical data.

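### The full-cohort 1-year mRS and EQ-5D models name no covariates although patients choose their treatment, and the SAP leaves open how deaths enter these comparisons

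*SAP*

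**What the plan says.** Treatment is not randomised: "The decision to select either medical treatment alone or additional endovascular recanalization is made by the patients themselves or their legal representatives" (SAP section 4, Study Design).

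For the primary outcome, SAP 7.5 (Primary Efficacy Outcome) states that "a multivariate Cox proportional hazards model will be used to perform multivariable adjustment for the primary outcome". SAP 7.7 (Secondary Outcomes) has no matching sentence. The 1-year mRS is to be analysed by ordinal logistic regression with a common odds ratio, and for quality of life "The 1-year EQ-5D scores will be compared between groups using general linear regression analysis". Protocol 3.16.2 names the same two models, again without covariates, and mentions adjusted estimates only as hazard ratios.

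Baseline function is recorded. Protocol 3.10.1 collects mRS and NIHSS at enrollment, and SAP 7.4 says that "baseline mRS score and NIHSS score, will be listed and summarized" by group. No model is said to use either score.

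Matching, 1:1 on a propensity score, "will be performed to reduce the possible influence of selection bias and confounders on the outcomes" (SAP 7.6, Propensity Score Matching Analysis; Protocol 3.16.4). The same outcome methods are used before and after matching. The covariates are described only as the main variables associated with the primary outcome.

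On the analysis set, SAP 7.2 ends its missing-data paragraph by saying that "only patients who entirely completed the 1-year follow-up are included in the final analysis". Multiple imputation is planned for the primary outcome only. Protocol Appendix 1 scores death as 6 on the mRS. Appendix 4 gives no EQ-5D value for death.

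**The concern.** There are two gaps.

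**Confounding.** Entry allows mRS 0 to 2 (Protocol 3.2.1), so groups formed by patient choice can start with different disability. Starting disability bears directly on mRS and quality of life a year later. With no covariates in either model, a baseline difference passes straight into the full-cohort estimate. If covariates are instead added once the data are in hand, their choice is not prespecified.

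**Deaths.** EQ-5D cannot be completed by a patient who has died. If one group has more deaths, the survivors' EQ-5D comparison does not show that harm. Unequal mortality is plausible on the protocol's own account: its Background expects recanalization in non-acute occlusion to carry raised procedural risk and more symptomatic intracranial hemorrhage. If the completers sentence also removed deaths from the mRS analysis, the one functional scale with a category for death would lose it.

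**Working it through.** The plan gives no sample size, mortality, EQ-5D mean or SD, so there is no figure of its own to reproduce. The check is first textual, then an illustration on assumed inputs.

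**1. Where adjustment is specified**

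| Analysis | Primary outcome | 1-year mRS | 1-year EQ-5D |
|---|---|---|---|
| Full-cohort model | Multivariable Cox, covariates not listed | No covariates named | No covariates named |
| Matched cohort | Same methods rerun | Same methods rerun | Same methods rerun |
| Basis for matching variables | Association with primary outcome | Same set | Same set |

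The matched analysis is therefore the only stated confounding control for mRS and EQ-5D. Its variables are selected for a stroke-or-death composite, and nothing guarantees that baseline mRS or NIHSS is among them. Baseline EQ-5D cannot be used: neither Table 1 nor Protocol 3.10.1 collects it.

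**2. What happens to deaths**

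- If the completers rule removes deaths, both outcomes become survivor comparisons and mRS 6 is lost.
- If the rule keeps deaths, mRS is complete. EQ-5D still has no value for these patients and no imputation is planned for it, so a linear model leaves them out.

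EQ-5D is a survivors' comparison on both readings. mRS is one only on the first.

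**3. Size of the EQ-5D death question (all inputs assumed)**

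Let survivors in both groups have the same mean m, and let mortality be dE (recanalization) and dM (medical). The survivors-only difference is 0. With death scored 0 the difference is m(1 − dE) − m(1 − dM) = −m(dE − dM).

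| dE vs dM | m = 0.80 | m = 0.90 |
|---|---|---|
| 1% vs 1% | 0 | 0 |
| 3% vs 1% | −0.016 | −0.018 |
| 5% vs 3% | −0.016 | −0.018 |
| 5% vs 1% | −0.032 | −0.036 |

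To set the shift against sampling error, assume m = 0.85, survivor SD 0.20, 150 per group, and mortality 6% vs 3%.

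- Shift: 0.85 × 0.03 = 0.0255.
- Variance with deaths as 0: (1 − d) × 0.20² + d(1 − d) × 0.85².
- At 6%: 0.94 × 0.04 + 0.06 × 0.94 × 0.7225 = 0.0783, SD about 0.28.
- At 3%: 0.97 × 0.04 + 0.03 × 0.97 × 0.7225 = 0.0598, SD about 0.245.
- SE = √((0.0783 + 0.0598)/150) ≈ 0.030.
- Ratio: 0.0255/0.0303 ≈ 0.84.

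**4. Size of the confounding question (assumed)**

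Shift = imbalance in a baseline factor × EQ-5D gap carried by that factor. Imbalances of 5 to 20 percentage points and gaps of 0.05 to 0.15 give 0.05 × 0.05 = 0.0025 up to 0.20 × 0.15 = 0.03.

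**5. Size of the mRS question if deaths were removed (assumed)**

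Take survivors in both groups at mRS 0 to 5 in proportions 0.35, 0.35, 0.15, 0.08, 0.05, 0.02. Without deaths the common OR is 1.00. A proportional-odds fit with deaths scored 6 gives an OR for a worse score of 1.07 at 3% vs 1% mortality and 1.14 at 5% vs 1%.

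**The case against.** The strongest reply is that matching already covers these outcomes. Its stated aim is not confined to the primary outcome, and the outcome methods are rerun in the matched cohort. A reader might infer from SAP 7.7 that mRS and EQ-5D receive no baseline adjustment anywhere; the documents do not support that. What stands is narrower: the full-cohort models are unadjusted, and the matching variables are unlisted and picked for a different outcome.

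A reader might also infer that the completers rule drops patients who died. SAP 7.2 does not say so. Excluding deaths would contradict the 30-day death component of the primary outcome and the 1-year mortality outcome, and SAP 7.2 itself censors event-free patients at death, which presupposes that they are in the data. The sentence may be aimed only at withdrawals and losses to follow-up. This objection stands in part: the wording is ambiguous, and that ambiguity needs removing. For mRS the scale already accommodates death, so no survivor problem arises unless the rule is applied literally.

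On size, keeping the survivor SD of 0.20 after adding zeros would give an SE of 0.20 × √(2/150) = 0.0231 and a ratio of 1.1. That understates the spread; 0.84 is the consistent figure. The illustration also sets survivors equal, so it shows only the mortality difference carried onto the EQ-5D scale. It is not evidence that the group with more deaths keeps healthier patients.

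Finally, scoring death as 0 is one defensible choice among several. Survivors' EQ-5D reported beside mortality is another. This is why it belongs in a sensitivity analysis.

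**Conclusion.** The point holds in this form. The full-cohort mRS and EQ-5D models name no covariates in a self-selected cohort, matching may not balance baseline disability, and the SAP does not settle how deaths are treated. EQ-5D is a survivors' comparison whichever way SAP 7.2 is read.

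On assumed inputs the effects are modest: 0 to about 0.036 on EQ-5D from deaths (0 when mortality is equal), 0.0025 to 0.03 from baseline imbalance, and an mRS common OR of 1.07 to 1.14 instead of 1.00 if mRS 6 were removed. The true direction and size depend on mortality and imbalance that the documents do not report. Two of the eleven secondary outcomes are affected. The missing covariates in these models do not touch the primary analysis. The completers wording reaches beyond these outcomes, but that is not assessed here. The change should be made, since the needed data are already collected.

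**What to change.** - **SAP 7.7 (Secondary Outcomes) and Protocol 3.16.2:** adjust both the mRS and EQ-5D models for baseline mRS and NIHSS plus the covariates of the primary multivariable model. List those covariates, since SAP 7.5 (Primary Efficacy Outcome) does not.
- **SAP 7.6 (Propensity Score Matching Analysis) and Protocol 3.16.4:** include baseline mRS and NIHSS in the propensity score.
- **SAP 7.2:** state that patients who die within 1 year are not removed by the completers rule and keep mRS 6.
- **SAP 7.7, EQ-5D:** say whether the index or the 0 to 100 rating is analysed. Label the comparison as one among survivors and report it beside 1-year mortality. Add a sensitivity analysis that scores death as 0 on the index, with a robust or bootstrap interval because the zeros skew the distribution.

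The cost is wording and a little extra programming, with no new data collection. Adding covariates to the propensity score may cost a few matched pairs.
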